## **Efficacy in MCL**

Study **PCI- 32765CLL1002** was an open-label drug-drug interaction study of 18 men, in which ibrutinib was administered alone at a 120 mg dose or in combination with ketoconazole at a 40 mg dose.  Results demonstrated that ketoconazole, a strong CYP3A4 inhibitor, increased ibrutinib exposure (Cmax and AUClast) by 29- and 24-fold, respectively. Terminal half-life was not increased. Ibrutinib single-dose administration was well-tolerated in Study PCI-32765CLL1002. No drug-related AEs were reported. No Grade 3 or 4 toxicities or SAEs were reported. 

Efficacy results from **Study PCYC-04753** and Study **PCYC-1104-CA** demonstrate that ibrutinib has activity as a single-agent in treatment of subjects with relapsed or refractory MCL.

Study PCYC-04753 was a Phase 1, multicentre, multi-cohort, open-label, dose-escalation study, in which 56 subjects with relapsed or refractory NHL including CLL and Waldenström's macroglobulinemia were enrolled across 7 dose cohorts. Nine of 56 subjects had a diagnosis of MCL and were evaluable for response. Seven of them achieved an objective response by the Revised Response Criteria for Malignant Lymphoma, including 3 CRs and 4 partial responses [PRs]; 1 subject had stable disease and 1 subject had progressive disease. All of the subjects responding to treatment achieved response at the time of the first post-baseline response assessment (after 2 cycles of treatment). Of the 3 subjects who achieved a CR, 2 subjects had CR on initial post-baseline assessment, and 1 subject achieved a PR initially and they had a CR after 8 cycles (28-days cycle duration) of therapy. Five subjects who entered a long-term follow-up study have durations of response ranging from 10.5 to 27.5 months.

This is an ongoing multicentre Phase 2 study in subjects with MCL who are relapsed or refractory to their previous treatment. Subjects are stratified based on their previous exposure to the chemotherapeutic agent bortezomib. The objectives include studying the efficacy of ibrutinib given as a continuous fixed dose of 560 mg/day. Preliminary results were recently presented on 68 subjects, of whom 51 were evaluable for efficacy. Overall best response (CR + PR) was 69%—71% among the bortezomib naive subjects (N = 31) and 65% among bortezomib-exposed subjects (N = 20). In some patients, treatment with ibrutinib was associated with a transient increase in peripheral lymphocyte count representing a compartmental shift of cells with the CD19+/CD5+ phenotype from nodal tissues to peripheral blood.

In a single arm ibrutinib monotherapy study conducted in patients with relapsed / refractory MCL an ORR of 67.6% a PFS rate of 63% (95% CI 53, 71%) at 6 months and a duration of response of 17.5 months were observed. In an update on time-dependent outcomes till March 2014, the beneficial effects were sustained. The treatment effect seemed fairly consistent throughout the analysed subgroups, including region, relapsed or refractory disease, bulky disease, number of prior regimens, simplified MIPI score, and prior therapy with bortezomib or lenalidomide.

The benefit- risk balance in the indication "treatment of adult patients with relapsed or refractory MCL" is considered positive, as outstanding activity is shown in terms of high response rate in this patient population of previously treated & relapsed or refractory MCL with an unmet clinical need, along with the added convenience of oral dosing once daily. With these results, ImbruvicaTM (Ibrutinib capsule 140 mg) has been approved in various regions of the world including India in patients with MCL who have received at least one prior therapy.

#### **Safety Overview**

Pooled safety data for subjects treated with ibrutinib monotherapy in 9 studies that have completed primary analysis as of the cutoff date for this Investigator's Brochure update (6 April 2015) (Studies 04753, 1102, 1112, 1117, 1104, MCL2001, 1106, 1118E, and JPN-101) are summarized below. The data presented also include subjects enrolled in Studies 1112 (N=57) and CLL3001 (N=90) who crossed over from ofatumumab or placebo, respectively, to receive treatment with ibrutinib monotherapy after progression and/or positive interim analysis results. Median duration on treatment was 8.3 months (range: 0.0 to 32.3 months).

Treatment-emergent AEs in more than 10% of subjects receiving ibrutinib as monotherapy (N=1071) The most frequently reported treatment-emergent AEs were diarrhea, fatigue, nausea, cough, anemia, pyrexia, and neutropenia.

Treatment-emergent AEs assessed as related to ibrutinib by the investigators in more than 5% of subjects receiving ibrutinib as monotherapy (N=1071). Adverse events that were considered by the investigator to be related to ibrutinib monotherapy were reported in 75.5% of subjects. The most frequently reported AEs related to ibrutinib were diarrhea, fatigue, neutropenia, and nausea.

Treatment-emergent AEs of Grade 3 or 4 in severity in more than 2% of subjects receiving ibrutinib as monotherapy (N=1071). Adverse events of Grade 3 or 4 were reported in 49.3% of subjects. The most commonly reported Grade 3 or 4 AEs that were hematologic in nature were neutropenia, thrombocytopenia, and anemia. Pneumonia, hypertension, and atrial fibrillation were the most frequently reported nonhematologic Grade 3 or 4 AEs.

The incidence of treatment-emergent SAEs reported in more than 1% of subjects receiving ibrutinib as monotherapy (N=1071). Serious AEs were reported in 43.2% of subjects. The most frequently reported SAEs were pneumonia, atrial fibrillation, febrile neutropenia, and pyrexia. The most frequently reported SAEs (any grade) that were considered related to ibrutinib were pneumonia, atrial fibrillation, and febrile neutropenia.

Among the 1071 subjects in the pooled analysis of monotherapy studies, 11.8% discontinued ibrutinib therapy due to an AE. The most frequently reported AEs leading to treatment discontinuation included infections (ie, pneumonia [1.4%] and sepsis [0.8%]), respiratory failure (0.6%), and subdural hematoma (0.5%). Fatal AEs were reported in 9.3% of subjects during study treatment or within 30 days of discontinuation of treatment. The most frequently reported causes of fatal AEs included pneumonia (1.7%), sepsis (0.7%), progressive disease (MCL [0.7%] in

subjects from MCL studies, CLL [0.6%] and Richter's syndrome (0.4%) in subjects from CLL studies).

Upon initiation of treatment, a reversible increase in lymphocyte counts (i.e.  $\geq$  50% increase from baseline and above absolute count 5000/mcL), often associated with reduction of lymphadenopathy, has been observed in most subjects (approximately 69% to 75%) with CLL/SLL treated with single agent ibrutinib. This effect has also been observed in some patients (33%) with MCL treated with single agent ibrutinib. This observed lymphocytosis is a pharmacodynamic effect and should not be considered progressive disease in the absence of other clinical findings. In both disease types, lymphocytosis typically occurs during the first few weeks of ibrutinib therapy (median time 1.1 weeks) and typically resolves within a median of 8.0 weeks in subjects with MCL and 18.7 weeks in subjects with CLL/SLL.

Lymphocytosis appeared to occur in lower incidence and at lesser magnitude in subjects with CLL/SLL receiving ibrutinib in combination with chemo-immunotherapy (i.e. 27% of subjects receiving ibrutinib + BR in Study 1108) or immunotherapy (i.e. 55% of subjects receiving ibrutinib plus of atumumab in Group 2 of Study 1109).

There were isolated cases of leukostasis reported in subjects treated with ibrutinib. A high number of circulating lymphocytes (> 400000/mcL) may confer increased risk. Subjects should be closely monitored. Administer supportive care including hydration and/or cytoreduction as indicated.

There have been reports of haemorrhagic events in subjects treated with ibrutinib in both monotherapy and combination clinical studies. The majority of these haemorrhagic AEs were of Grade 1 or 2 in severity; those included contusion, epistaxis, and petechiae. Haemorrhagic events of Grade 3 or higher, including central nervous system (CNS) haemorrhage of any grade severity, occurred in 3.4% (17/506) of subjects treated in monotherapy studies and in 3.1% (4/130) of subjects treated in combination therapy studies; none were reported in the healthy volunteer studies (N=100). In the extension study, PCYC-1103-CA, two additional Grade 3 events associated with bleeding were reported ('gastrointestinal haemorrhage' and 'haematotympanum'). It is not clear whether or not these events are attributable to ibrutinib. Subjects were excluded from participation in specific ibrutinib Phase 2 and 3 studies if they required warfarin or other vitamin K antagonists.

However, it is possible that treatment with ibrutinib could increase the risk of bruising or bleeding. Subjects in the current study will be monitored closely for haemorrhagic AEs. Guidance on use of antiplatelet agents and anticoagulants is provided in locally approved prescribing information.

Infections (including sepsis, bacterial, viral, or fungal infections) were observed in subjects treated with ibrutinib therapy. In non-randomized clinical trials, infections (including sepsis, bacterial, viral, or fungal infections) were observed in subjects with MCL (≥Grade 3; 25.2%) and CLL/SLL (≥Grade 3; 37.6%). Some of these infections have been associated with hospitalization and death. Although causality has not been established, cases of progressive multifocal leukoencephalopathy have occurred in subjects treated with ibrutinib. Treatment-emergent Grade 3 or 4 cytopenias (neutropenia, thrombocytopenia, and anaemia) were reported in subjects treated with ibrutinib.

Subjects should be monitored for fever and infections and appropriate anti-infective therapy should be instituted as indicated.

Atrial fibrillation and atrial flutter have been reported in subjects treated with ibrutinib, particularly in subjects with cardiac risk factors, acute infections, and a previous history of atrial fibrillation. Periodically monitor subjects clinically for atrial fibrillation. Subjects who develop arrhythmic symptoms (e.g., palpitations, lightheadedness) or new onset of dyspnea should be evaluated clinically, and if indicated, have an ECG performed. For atrial fibrillation which persists, consider the risks and benefits of ibrutinib treatment and follow the dose modification guidelines as per Attachment 3 in conjunction with local prescribing information

Other malignant diseases have been observed in subjects who have been treated with ibrutinib, including skin cancers, adenocarcinomas, and other hematologic malignancies. It is not clear whether or not these events are attributable to ibrutinib. Subjects in the current study will be monitored for other malignancies.

Tumour lysis syndrome has been reported with ibrutinib therapy. Subjects at risk of tumour lysis syndrome are those with high tumour burden prior to treatment.

Diarrhoea is the most frequently reported nonhaematologic AEs with ibrutinib monotherapy and combination therapy. Other frequently reported gastrointestinal events include nausea, vomiting, and constipation. These events are rarely severe and are generally managed with supportive therapies including antidiarrheal and antiemetic.

Mild to moderate rash has been commonly reported in subjects treated with either single-agent ibrutinib or in combination with chemotherapy. Rash occurred at a higher rate in the ibrutinib arm than in the ofatumumab arm in Study PCYC-1112-CA. Most rashes were mild to moderate in severity. One case of Stevens-Johnson Syndrome (SJS) was reported in a subject with CLL. The subject received ibrutinib (420 mg/day) and was also receiving various antibiotics and anti-gout medication (allopurinol) known to be associated with SJS. Subjects should be monitored closely for signs and symptoms suggestive of SJS.

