#### 4.2. Exclusion Criteria

Potential patients who meet any of the following criteria will not be eligible for this study:

- 1. Patients who are not eligible to receive ImbruvicaTM as per the locally approved prescribing information.
- 2. Patients participating or planning to participate in any interventional drug trial during the course of this study.

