## **Clinical Laboratory Tests**

Blood samples for hematology and coagulation profile will be collected as per protocol. The investigator must review the laboratory results, document this review, and record any clinically relevant changes occurring during the study in the adverse event section of the CRF. The laboratory reports must be filed with the source documents.

The following tests will be performed by the local laboratory

Hematology Panel

-hemoglobin

-hematocrit

-red blood cell (RBC) count

-platelet count

[-percent reticulocytes]

-absolute lymphocyte count (ALC)

-coagulation (PT, INR and aPTT)

-white blood cell (WBC) count with differential

Note: A WBC evaluation may include any abnormal cells, which will then be reported by the laboratory. A RBC evaluation may include abnormalities in the RBC count, RBC parameters, or RBC morphology, which will then be reported by the laboratory. In addition, any other abnormal cells in a blood smear will also be reported.

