#### 4.6. Prior and Concomitant Medications

Prior and Concomitant medications will be coded using the latest World Health Organization Drug Dictionary (WHO-DD). Prior medications are defined as any therapy used before the day of first dose (partial or complete) of study agent. Concomitant medications are defined as any therapy used on or after the same day as the first dose of study agent, including those that started before and continue on after the first dose of study agent.

The data on prior and concomitant medications will be listed separately for each subject.

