## 6.2. Clinical Laboratory Tests

The following summary tables will be presented by type of laboratory test:

- Descriptive statistics will be calculated for each laboratory analyte (Hematology and Coagulation) for observed values at each scheduled time point.
- Parameters with predefined National Cancer Institute Common Terminology Criteria for Adverse Events (NCI-CTCAE, Version 4) toxicity grades at each scheduled time point of measurement
- The number and percentage of subjects with NCI-CTCAE grade >= 3 (markedly abnormal) for the parameters with predefined NCI-CTCAE toxicity grades at each scheduled time point of measurement
- Subjects with abnormal laboratory values at all measured time point.
- Subjects with any markedly abnormal laboratory results
- Normal reference ranges.

Since there is no conventional baseline visit, the values and abnormalities will be summarized by visit without change from baseline analysis. But the sensitivity analysis will be performed with baseline defined as Visit 1.

- Descriptive statistics will be calculated for each laboratory analyte (Hematology and Coagulation) at baseline and for observed values and changes from baseline at each scheduled time point.
- Shift tables (cross-tabulations) summarizing the shift in laboratory values from baseline to the worst post baseline measurement experienced by the subject during the study with respect to NCI-CTCAE toxicity grades
- Shift tables (cross-tabulations) summarizing the shift in laboratory values for non-graded parameters from baseline to each scheduled time point of measurement with respect to abnormality criteria (low, normal, high).
- For all participants, a listing to support the sensitivity analysis table will be provided which will include clinical laboratory test results and change from baseline at all measured time points.

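### SAP 6.2 summarises PT, INR and aPTT without regard to anticoagulant use, so any intended anticoagulation would be counted as a laboratory abnormality on ibrutinib

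*Protocol*

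**What the plan says.** **Eligibility.** The Protocol's Safety Overview (section 1.2) reports that "Subjects were excluded from participation in specific ibrutinib Phase 2 and 3 studies if they required warfarin or other vitamin K antagonists". For the present study it says: "Guidance on use of antiplatelet agents and anticoagulants is provided in locally approved prescribing information". Section 4.2 has two exclusion criteria. One opens "Patients who are not eligible to receive Imbruvica" and continues by reference to that same prescribing information. The other is "Patients participating or planning to participate in any interventional drug trial during the course of this study". Neither names an anticoagulant. Section 8 asks that all concomitant drugs be recorded with name, dose and start/stop dates.

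**Measurement.** Protocol 9.2 (Clinical Laboratory Tests) includes PT, INR and aPTT, done at the local laboratory.

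**Analysis.** SAP section 6 puts safety analyses on all treated subjects unless otherwise specified. SAP 6.2 plans: "Descriptive statistics will be calculated for each laboratory analyte (Hematology and Coagulation) for observed values at each scheduled time point". It also plans a summary described as "Subjects with abnormal laboratory values at all measured time point", and counts of Grade 3 or higher values where CTCAE grades exist. The SAP amendment history records that laboratory data were not captured before dosing. The main laboratory tables therefore carry no change from baseline, and a sensitivity analysis takes Visit 1, already on treatment, as baseline. On co-medication, SAP 4.6 says: "The data on prior and concomitant medications will be listed separately for each subject". Nothing links those drugs to the coagulation results.

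**The concern.** A vitamin K antagonist is given in order to raise INR. In tables that ignore co-medication, that effect appears as an out-of-range value on ibrutinib. This design offers little to separate the two. There is no control arm and no pre-dose INR. With Visit 1 as baseline, an anticoagulant started before Visit 1 is absorbed into the baseline, while one started later appears as a shift during ibrutinib treatment.

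The coagulation tables matter here. The Protocol synopsis names laboratory tests as safety variables beside adverse events, and coagulation is one of only two laboratory groups in SAP 6.2. The Safety Overview gives haemorrhage of Grade 3 or higher (with CNS haemorrhage of any grade) in 17/506 = 3.4% of monotherapy subjects and says that ibrutinib could increase the risk of bruising or bleeding. A reader will look to these tables for evidence on clotting, and unmarked anticoagulation would blur what they show.

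**Working it through.** The plan gives no figure on this point to reproduce. The sample size of 75 is a committee recommendation with no rate or precision behind it. The following is therefore an illustration of scale.

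**Inputs**
- n = 75 (Protocol 11.2, SAP 1.4).
- Assumed, not in the documents: INR without an anticoagulant has mean 1.05, SD 0.10; on a vitamin K antagonist, mean 2.5, SD 0.4.
- k = number of subjects on a vitamin K antagonist at a visit. It is unknown; 0, 2, 4 and 8 are shown.

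**Step 1: mean, SD and median at one visit.** With p = k/75:
- mean = [(75 − k) × 1.05 + k × 2.5] / 75
- variance = (1 − p) × 0.10² + p × 0.4² + p(1 − p) × (2.5 − 1.05)²
- median: the value below which a fraction 0.5/(1 − p) of the untreated normal distribution lies

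For k = 4: mean = (74.55 + 10)/75 = 1.127. Variance = 0.018 + 0.0533 × 0.9467 × 2.1025 = 0.018 + 0.106 = 0.124, so SD = 0.35.

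| k | k/75 | mean | SD | median |
|---|---|---|---|---|
| 0 | 0% | 1.05 | 0.10 | 1.050 |
| 2 | 2.7% | 1.09 | 0.26 | 1.053 |
| 4 | 5.3% | 1.13 | 0.35 | 1.057 |
| 8 | 10.7% | 1.21 | 0.48 | 1.065 |

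**Step 2: abnormal counts.** One subject is 1/75 = 1.3 percentage points. That is the most each can add, since some would have been out of range anyway.

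**Step 3: what share of the abnormal count would this be?** It depends on the upper reference limit, which the documents do not state. Expected numbers of untreated subjects above an assumed limit are (75 − k) × P(INR > limit):

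| assumed limit | untreated above limit | k = 2 | k = 4 | k = 8 |
|---|---|---|---|---|
| 1.1 | 30.9% | 22.5 | 21.9 | 20.7 |
| 1.2 | 6.7% | 4.9 | 4.7 | 4.5 |
| 1.3 | 0.6% | 0.5 | 0.4 | 0.4 |

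At 1.3 the anticoagulated subjects are most of the flagged ones for every k above 0. At 1.2 they are so only for k = 8, and at 1.1 never.

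**Step 4: how likely is at least one?** If a share s of patients uses such a drug, the chance is 1 − (1 − s)^75, which is 78% for s = 2%, 98% for 5% and above 99% for 10%. These shares are assumptions too. At s = 0 the point has no effect.

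**The case against.** **Eligibility.** A reader might infer that vitamin K antagonist users are admitted here. The documents do not show that. The first exclusion criterion defers to prescribing information that also carries the anticoagulant guidance and that we cannot see. The supportable statement is that they are not explicitly excluded. The earlier exclusion was also narrow: vitamin K antagonists, in specific studies, not anticoagulants in general. Neither limit reaches a drug started after entry.

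**Existence.** No document says that any subject is on such a drug. The Protocol names atrial fibrillation as an ibrutinib risk but does not connect it with anticoagulation, so it supports no count. This stands, and the point is conditional.

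**Attribution.** SAP 6.2 is descriptive and assigns no cause. Causality is judged for adverse events, where the Protocol 12.1.2 definitions from Doubtful to Very Likely all weigh concomitant drugs. Only clinically relevant laboratory changes become adverse events (9.2). It would be too strong to say that the primary endpoint is biased.

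**Existing displays.** The SAP also reports median, minimum and maximum. The median is nearly unaffected, and the maximum would reveal outliers. Medications and laboratory values are both listed, so about 75 subjects could be matched by hand. That is true, but the abnormal counts and shift tables would remain mixed, and a reader of the tables alone would not know it.

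**Actual use.** The objective is safety under actual conditions of use. Making off-anticoagulant samples the main table would condition on a post-treatment variable and move co-medicated patients out of the headline rows. This objection is sound, and the fix below respects it.

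**Conclusion.** The point holds in conditional form. SAP 6.2 mixes coagulation results from subjects on and off anticoagulants, and nothing else in the main tables can separate an intended anticoagulant effect from an effect of ibrutinib. If such subjects are enrolled, or start such a drug on study, their out-of-range values would be counted as abnormalities on ibrutinib.

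Under the assumed INR values, 2 to 8 such subjects raise the mean by 0.04 to 0.15 and increase the SD about 2.6- to 4.8-fold (0.26/0.10 to 0.48/0.10). They make up 2.7% to 10.7% of the 75. With none, nothing changes.

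Three stronger readings are not supported:
- That these subjects would supply most of the abnormal INR values: this turns on an unstated reference limit and on k.
- That Grade 3 or higher counts would be inflated: the CTCAE text is not in the documents, so its handling of anticoagulated subjects cannot be checked.
- That the primary adverse event result is compromised: attribution there already weighs co-medication.

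The missing pre-dose value is a separate limitation, which the SAP states openly and which this fix does not cure.

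**What to change.** In SAP 6.2, derive a flag for each PT, INR and aPTT sample that shows whether an anticoagulant was ongoing on the sample date. Use the coded drug names and the start/stop dates already collected (Protocol 8, SAP 4.6). State in advance which coded drugs count and how partial dates are handled. Keep the all-subject coagulation tables as they are. Add rows for samples on and off anticoagulants to the descriptive summaries, the abnormality counts and the shift tables that use Visit 1 as baseline.

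The cost is one derived variable, a short addition to the SAP and some rows with small counts. No new data are needed, no sample is discarded, and neither eligibility nor clinical management changes.
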